9.5.2 Secondary/Distal Outcomes

Consistent with the U01 mechanism, our focus in this study is NOT on the distal outcomes; rather, it is on yoga dosage received. However, we will collect distal outcome data to demonstrate feasibility of data collection for future research. Distal outcomes include: Pain interference, Pain Severity, Quality of Life, Depression, Anxiety, Substance Use, Retention in OAT, and Opioid Craving. The primary outcome for a future efficacy study will be pain interference.

9.6 Data Analyses

Phase 1 Data Analysis: See Section 9.5.1

Phase 2 Data Analysis: We plan to assess 4 candidate intervention components for possible inclusion in an optimized intervention that will be evaluated in a future RCT. To do so, we will use a balanced factorial ANOVA illustrated in Table 2. Each component will have two conditions producing a $2^4 = 16$ cell design with 4 main effects, 6 possible 2-way interactions, 3 possible 3-way interactions, and 1 possible 4-way interaction. In a fully balanced design using effect coding (not dummy coding), all effects in the model are uncorrelated and the n for each condition for all effects is N/2 (i.e., 96 without attrition; 79 estimated with 17% attrition for this primary outcome). Note that specific cells are not compared against other specific cells.

We will use a general linear model with each candidate component coded using effect (1 vs -1) coding. Recruitment site, sex, age, and OAT type will be covariates. The pragmatic exigencies of field research will likely result in imperfect balance (e.g., individual cells may have slightly varying n). However, we anticipate only very small variations in cell sizes and thus estimated model coefficients will be nearly, but not perfectly, uncorrelated.

To augment traditional frequentist statistics and facilitate interpretation we will calculate the Bayes factor. Based on the observed data, a Bayes factor estimates the strength of evidence supporting one hypothesis (model) in favor of a competing hypothesis (model).³²

We will track which classes each participant attends, and who teaches each class. As a sensitivity analysis, we will include not only site as a fixed effect, but also teacher. We will include a dummy variable for each teacher to represent whether or not the participant had exposure to that particular teacher (i.e., took at least one class with that teacher).

Determination of Final Intervention Components:

Goal: To determine which components will be included in the final, optimized intervention package.

Components:

All participants: attendance at 1 class (with 2 time choices) per week; materials for personal practice

1. Personal practice videos featuring study yoga teachers
2. Initial and 1-month 1:1 session with a yoga teacher
3. Text messages cuing personal practice
4. Monetary incentives for class attendance

Once data collection is complete, we will convene a meeting (or conference call) to make decisions about which intervention components should be included in the final intervention package. Participants in this meeting will include:

1. MPIs and co-Is and consultant [name];
2. Selected NCCIH staff (e.g., PO); and
3. Selected yoga instructors

At this meeting we will review all data collected.

Step 1: For each intervention component, we will first review the main and 2nd order interaction effects from the factorial experiment on the primary outcome of number of yoga minutes per week. We assume data will be missing at random. Missing data will be addressed using multiple imputation by chained equations.³³ Because the goal is intervention optimization, retention of components will not be based on a single criterion. We will initially choose to include all components for which there is a main or sympathetic interaction effect with a) an effect size (SMD) of 0.40 (estimated, based on preliminary data, to be 31 mins of yoga per week) or greater favoring the component; OR b) $p < .10$ favoring the component OR c) if the estimated Bayes factor provides substantial or stronger evidence preferring the intervention hypothesis to the hypothesis of no treatment effect. (See below for more information on Bayes factor).

Special cases:

1. Of monetary incentives for class attendance, we will look specifically at class attendance. If monetary incentives increase class attendance, and do not decrease overall minutes of practice, we will choose to include.
2. 3rd and 4th order interactions may be tricky to interpret. We will look at them, but place priority on main effects and 2nd order interactions in making decisions.
3. It is possible that 2nd order interactions may be antagonistic where the combination of two or more components is less effective than would be expected based on the main effects alone. At the same time, there may be significant positive main effects for both components. In this case, we will examine graphical depictions of results in order to determine whether to include both of the two components in question.

Step 2: All components that pass Step 1 will then be examined in light of their feasibility and acceptability. Data that bear on feasibility and acceptability include:

1. Participants' responses to qualitative interviews
2. Yoga instructors' experiences (field notes)
3. Feedback from administrators/ clinicians at sites [from field notes (clinicians) and structured interviews (key administrators)]
4. Adverse events determined to be related to a given component
5. Number of 1:1 sessions attended (relevant for the 1:1 session intervention component only); use of personal practice videos (relevant for the personal practice video component only). We note that even one 1:1 session, or a small amount of use of personal practice videos, could have an impact on pain interference or other relevant outcomes.
6. % of follow-up assessments completed (not expected to be different between groups; we would consider a difference of 15% in proportion of participants observed at M3 to be of concern, and would likely be a statistically significant difference)

In determining feasibility, each component that passed Step 1 will be determined to be:

1. Acceptable and feasible without any changes.
2. There are minor changes that we judge do not affect the core nature of the intervention that we can make to increase acceptability and feasibility to a higher level (e.g., 1:1 meetings were scheduled for 45 minutes but everyone agrees that 30 minutes was adequate and even preferable).
3. Not acceptable/ feasible.

Step 3. All components that passed Step 1 and Step 2 will be included in the final optimized intervention. We will make minor changes to components if indicated in Step 2.

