5. STUDY INTERVENTIONS

5.1 Interventions, Administration, and Duration

Standard Yoga classes are administered to a group of participants. All participants will receive the standard yoga class intervention. Participants will be invited to attend one yoga class per week. Classes may be offered at multiple timeslots. Classes will take place at the clinic/facility where they receive OAT or via a secure video-based platform such as Zoom; they are planned to be 60 minutes long. Registered yoga teachers will deliver the intervention. Potential risks include loss of privacy or breach of confidentiality, increased distress or physical pain due to procedures, ineffective intervention (i.e., lack of improvement in physical pain symptoms), and mild physical injury.

Components of Yoga Intervention are delivered to participant individually based on randomization assignment. Components include: 1) Personal practice videos featuring study yoga teachers, 2) 1:1 session with yoga teacher at baseline and 1 month (in-person or via a secure video-based platform), 3) Text messages cuing personal practice, 4) Monetary incentives for class attendance. Potential risks include loss of privacy or breach of confidentiality, increased distress or physical pain due to procedures, ineffective intervention (i.e., lack of improvement in physical pain symptoms), and mild physical injury.

COVID-related adjustments. Due to COVID restrictions, we may not be able to offer

classes or 1:1 sessions with yoga teachers in-person. Thus, we will offer classes and meetings via a secure video-based platform on study-provided cell phones. Whether interventions are via a secure video-based platform or in person may fluctuate during Phase 1 of the study. Prior to the start of Phase 2, we will decide on the best modality to provide interventions for Phase 2, and then stay with that modality throughout the duration of Phase 2, barring unforeseen circumstances.

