9.5 Outcomes

9.5.1 Primary/Proximal Outcome

Phase 1 is a pilot study to assess feasibility. The primary aims and outcome assessments are shown in Table 4 below.

Table 4. Targets for Phase 1 Pilot Study.		
Feasibility Area	Method of assessment	Target at each site
Recruit participants	Number recruited per month	Recruit 10 participants in 4 months.

Train yoga teachers to fidelity	Teacher fidelity scale	Each teacher demonstrates >80% fidelity on final 3 classes rated.
Randomize participants to intervention components and correctly administer these components	Randomization errors; receipt of incorrect intervention components	No errors/ incorrect components received in 2 nd half of participants randomized.
Collect follow-up assessments	Percent of follow-up assessments collected (for M1, M2, and M3)	≥ 70% with sufficient data collected on dosage; ≥ 70% of other follow-up assessments collected, including chart reviews

The proximal outcome of Phase 2 is yoga dosage received. This will be calculated by adding total number of minutes per week in the study yoga class and total number of minutes per week in personal practice (or outside yoga classes). Research staff will take attendance at study yoga classes, and, in the event someone does not attend the entire yoga class, will record the number of minutes present in class. We will measure personal practice using the Weekly Personal practice Questionnaire.

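### The teacher sensitivity model adjusts for attendance after randomisation, so it generally shrinks the incentive effect (Component 4) even if teachers make no difference

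*Combined protocol and SAP*

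**What the plan says.** Section 9.6 (Data Analyses) fits a general linear model to dosage, with the four components effect-coded and recruitment site, sex, age and OAT type as covariates. It then adds: "As a sensitivity analysis, we will include not only site as a fixed effect, but also teacher". The implementation is: "We will include a dummy variable for each teacher to represent whether or not the participant had exposure to that particular teacher". A single class with a teacher sets that teacher's dummy to 1. No rule is given for reading a change in the component estimates.

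Section 9.5.1 defines dosage: "This will be calculated by adding total number of minutes per week in the study yoga class", plus minutes of personal practice or outside classes. The class part comes from the attendance record: "Research staff will take attendance at study yoga classes". Under section 5.2, Component 4 pays $15 for each class attended, and each site has at least two trained teachers.

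Nothing ties a participant to one teacher. Section 5.1 says "Classes may be offered at multiple timeslots", and section 9.6 describes "attendance at 1 class (with 2 time choices) per week". On the selection meeting, section 9.6 says "At this meeting we will review all data collected" and, in Step 1, "Because the goal is intervention optimization, retention of components will not be based on a single criterion".

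**The concern.** A participant's dummies are determined by which classes that participant attended after randomisation. Someone who never attends has every dummy at 0 and zero class minutes. If teachers rotate, frequent attenders collect more dummies at 1. For the class-minutes part of dosage, the model therefore adjusts the outcome for a coarse version of itself, and that coarse version lies downstream of the randomised component.

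The effects at risk are those that act through attendance: chiefly Component 4, and any other component so far as it changes attendance. If motivation to attend is also related to home practice, conditioning on attendance adds a second distortion to the home-practice part, because participants with equal exposure in the two arms then differ in motivation.

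A sensitivity analysis for teacher should stay still when teachers do not matter. This one can move, so a smaller Component 4 estimate cannot be read as lack of robustness to teacher. The selection group could see such a result with nothing to warn them.

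**Working it through.** **The plan's own figures.** The plan gives no figure for the teacher model. Its scale and sample size can be checked.

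- Section 9.6, Step 1: an SMD of 0.40 equals 31 min/week, so SD = 31/0.40 = 77.5 min/week.
- Section 9.2: n = 192 − 34 = 158, or 79 per level. Power ≈ Φ(d·√(79/2) − 1.645) at two-sided 0.10. For d = 0.40: Φ(2.514 − 1.645) = 0.808. For d = 0.50: Φ(3.142 − 1.645) = 0.933. Both match the stated figures (above .80 and above .90).

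**A hand example, one teacher per participant.** Assume that never-attending falls from 25% to 15% under the incentive, that overall attendance rises from 30% to 45%, and that classes last 60 minutes weekly.

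1. Unadjusted: 0.45×60 − 0.30×60 = 27 − 18 = 9.0 min/week.
2. Among ever-attenders: 27/0.85 − 18/0.75 = 31.8 − 24.0 = 7.8. Among never-attenders the difference is 0 by definition.
3. Least squares with an exposure dummy weights each stratum by (share in one arm × share in the other)/(sum of shares). Ever: 0.75×0.85/1.60 = 0.398. Never: 0.25×0.15/0.40 = 0.094.
4. Adjusted: 7.8 × 0.398/(0.398 + 0.094) = 6.3 min/week, a loss of about 30% with no teacher effect anywhere.

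If the never-attending share were exactly equal in both arms, this one-teacher example would show no loss. In practice some willing participants attend no class by chance, more of them without the incentive. With rotating teachers, the number of teachers met also rises with attendance.

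**Simulation.** The design was 2⁴ with 12 weekly 60-minute classes and no teacher effect. Least squares used ±1 components and site, with and without the dummies, on 400,000 or 800,000 simulated participants per scenario. Assumptions, none from the documents:

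- attendance over all participants of 20–50% without Component 4 and 15 points higher with it (0.15×60 = 9 min/week);
- 20% never attending in both arms;
- logit SD of motivation 1.0; home-practice SD 70, giving a total SD of 73–77.

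Teachers by site were 2+2 (the section 5.2 minimum), 3+2, or 3+1 (the instructor count in section 6.2.3). Component 4 on class minutes, 2+2 teachers:

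| Attendance without incentive | One teacher kept | Teachers rotate |
|---|---|---|
| 20% | 9.0 → 7.1 (21% loss) | 9.0 → 5.0 (44%) |
| 30% | 9.0 → 8.0 (11%) | 9.0 → 6.1 (32%) |
| 50% | 9.0 → 8.8 (2%) | 8.9 → 7.9 (11%) |

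Percentages in the table come from the rounded minutes and can differ by a point from the ranges below.

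- All teacher layouts: 7.1–8.9 with one teacher (loss about 1–21%); 4.3–7.9 rotating (12–52%).
- Gain 10–20 points, never-attending 10–25%: loss 0–26% and 9–60%.
- Incentive cuts never-attending from 25% to 15%, gain still 15 points: loss 37–49% and 51–64%.
- Total dosage: about the same loss as for class minutes if motivation and home practice are unrelated. With correlation 0.3 the loss is 2–30% (one teacher) and 15–87% (rotating).
- A 31 min/week effect acting only through home practice: adjusted/unadjusted ratio 0.998–1.003.

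**Other assumptions, same direction.** A second simulation used N = 192, attendance pairs from 15/30% to 60/80%, logit SD 0.5 or 1.5, and two or three teachers per site who rotated, were mostly tied to a slot, or (two teachers only) were fixed. Component 4 on class minutes shrank in 39 of 40 combinations, by up to 75%. The exception was 60/80% attendance, low heterogeneity and a fixed teacher, with 0% loss.

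**At the planned n = 158** (2+2 rotating, 30% without incentive, 2,000 trials):

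- Class minutes: 9.1 (SE 2.8) → 6.2 (SE 1.8); chance of p < .10 goes from 0.94 to 0.97.
- Total dosage: 8.9 (SE 11.6) → 6.0 (SE 11.6); chance of p < .10 goes from 0.21 to 0.16.

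**The case against.** The strongest reply is that no stated decision rule uses this model. Step 1 rests on the factorial effects, Special case 1 judges incentives on class attendance itself, Step 2 does not list the teacher model, and Step 3 follows from the first two. The sentence about not relying on one criterion introduces three listed criteria and need not open the door to any other analysis. Component 4's assumed effect is 9/77.5 = 0.12 SD, which fails the 0.40 criterion either way, and p-values barely move.

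The sizes are also almost wholly assumed. The simulations with a motivation–home-practice link used positive correlations. With −0.3 (2+2 rotating, 20% attendance) the total-dosage loss drops from 44% to about 16%. The 3+1 layout conflicts with the two-per-site minimum in section 5.2, and its count comes from a blinding table rather than a teaching rota.

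Much of this stands. The consequence is limited to interpretation, and the size cannot be known from the documents. The direction is not answered: the negative correlation reduced the loss without reversing it, and the 2+2 results do not depend on the disputed layout. Nor does being a sensitivity analysis rescue the model, because it can shift when the thing it tests for is absent.

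**Conclusion.** The concern holds. As specified, the teacher model conditions on a consequence of the randomised components and cannot show whether attendance-driven effects are robust to teacher. The bias is generally toward zero and falls chiefly on Component 4. Under the main assumptions the loss on class minutes is about 1–21% with one teacher per participant and 12–52% with rotation. It is negligible when attendance is high and each participant keeps one teacher, and larger if the incentive also reduces never-attending. These sizes rest on assumed attendance, rotation and motivation.

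The distortion is in the estimate more than in the p-value. The primary model, the Step 1 criteria, Special case 1 and effects acting only through home practice are unaffected. It is worth correcting, but it does not threaten the main analysis.

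**What to change.** In section 9.6, stop using the attendance-defined dummies as a robustness check on component effects for total dosage or class attendance. Then choose one of these:

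1. **Report teacher exposure descriptively**: classes attended per teacher, by component and site. The plan already tracks who attends and who teaches each class, so this needs no new data.
2. **Keep the model for personal-practice minutes only**, label it exploratory, and state that it conditions on post-randomisation attendance. Add that a component which changes attendance can still be shifted. With a true Component 4 effect of 0 on home practice and correlation 0.3, the simulated shift is 0 to −0.8 min/week (one teacher) and −0.1 to −3.2 (rotating).

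Either is a wording change. The cost is that there may be no teacher-adjusted estimate for attendance-driven effects.

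If a class slot with a fixed teacher were recorded before randomisation, the scheduled teacher could serve as the covariate. The documents do not now provide this: inclusion criterion 6 (section 4.1) covers availability only, and no section ties a teacher to a slot. It would need one added baseline field and fixed slots, and would measure actual contact less closely. It is optional.

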6.2.3 Blinding

Follow-up assessments will be conducted by research staff who are blind to which arm participants were randomized. See table on next page.

Personnel	Role	Site	Blind?	Description of activities/ reason for status
[name]	MPI	Butler	Yes	
[name]	Co-I	Butler	No	Will serve as an Investigator who is not blind, and available to consult with project manager or other staff about a) SAE reports that may relate to randomization; b) other randomization-related activities or problems
[name]	Project manager	Butler	No	Will supervise randomization, conduct unblinded data audits at both sites, and prepare unblinded reports
[name]	Project manager	Butler	No	Will supervise randomization, conduct unblinded data audits at both sites, and prepare unblinded reports
[name]	Study statistician	Butler	Yes	
[name]	Data manager	Butler	Yes	Will work with [name] to provide blinded reports; will serve as back-up to blind RA at CODAC
TBN	Research assistant	Butler	Yes	Will assist with recruitment (pre-randomization) and conduct follow-up assessments at CODAC
TBN	Research assistant	Butler	No	Will recruit participants and facilitate randomized intervention components at CODAC
TBN	Consultant --Lead yoga instructor	Butler	No	Will provide supervision to yoga instructors re: 1:1 visits
[name]	Consultant – MOST expert	Butler	Yes	
TBN	Yoga instructors (n=3)	Butler	No	Providing 1:1 visits
[name]	MPI	BU	Yes	
[name]	Site PI	CODAC	Yes	
[name]	Site coordinator	CODAC	No	Will serve as back-up to non-blind RA at CODAC
[name]	CFO/ research administration	CODAC	Yes	
[name]	Co-I	RIH	No	Will provide supervision to yoga instructors re: 1:1 visits
[name]	Site PI	BMC	Yes	Oversee all recruitment, eligibility, consent, intervention, and data collection activities at BMC
[name]	Co-I	BMC	Yes	Primary role in recruitment and consultation regarding any issues related to OAT treatment and eligibility
[name]	Project manager	BMC	Yes	Subcontracts, invoices, oversee research staff
TBN	Research assistant	BMC	Yes	Will assist with recruitment (pre-randomization) and conduct follow-up assessments

TBN	Research assistant	BMC	No	Will recruit participants and facilitate randomized intervention components
[name]	Yoga instructor	BMC	No	Providing 1:1 visits

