Study staff will record all reportable events with start dates occurring any time after informed consent is obtained at least until the final day of study participation. Each time participants attend a yoga class, we will inquire about injuries due to yoga. For all participants in either the Phase 1 or 2, at Month 3 (end of intervention), study staff will administer the SAFTEE in order to inquire about the occurrence of AE/SAEs during the previous 3 months. This allows us to systematically assess number of adverse events, severity, and resulting impairment. Finally, any time a participant reports an adverse event to any staff member, a research assistant will contact the participant to ascertain information for recording of the adverse event. For adverse events ascertained by any of these three possible methods, the research assistant gets information on what happened, start and stop dates, severity, functional impact, interactions with healthcare professionals, perceived cause, and possible relation to study participation. With this information, [name] or [name], with input from Drs. [name] or [name], will code severity, causal relationship, and whether the event was expected. If necessary, staff will seek further information from the participant or other sources before coding. AEs will be coded on a weekly basis. Any potential SAE will be immediately reviewed by one of the MPIs or site PIs (or a qualified designee in their absence) and coded; this coding will subsequently be reviewed by the Safety Monitoring Committee (SMC).

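### Step 2 weighs only adverse events attributed to a component, and no on-versus-off comparison of adverse events or injuries by randomised component is planned

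*Combined protocol and SAP*

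**What the plan says.** Section 9.6 of the combined protocol and SAP selects components in steps. Step 1 looks at yoga minutes. Step 2 examines the surviving components for feasibility and acceptability, using six kinds of data. Item 4 is the only one that names adverse events: "Adverse events determined to be related to a given component". It gives no rate, denominator, comparison or method of determination. Item 6 of the same list does compare groups, on follow-up completion: "we would consider a difference of 15% in proportion of participants observed at M3 to be of concern".

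Section 7.2, whose title covers the analysis of safety parameters, only refers to Table 2. That table lists how and when events are assessed and what staff then do.

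Section 7.3 requires adverse events to be recorded whatever their relationship to the intervention. The information gathered on each event includes "perceived cause, and possible relation to study participation". Designated staff, whose names are removed from the public text, "will code severity, causal relationship, and whether the event was expected". For serious events: "Any potential SAE will be immediately reviewed by one of the MPIs or site PIs (or a qualified designee in their absence) and coded". The table in section 6.2.3 lists both MPIs and both site PIs as blind. It also lists an unblinded co-investigator whom staff may consult on SAE reports with a possible link to randomisation, and unblinded project managers who produce unblinded reports.

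**The concern.** The four components are study videos, two 1:1 sessions, text cues and $15 per class attended. All are meant to increase yoga dosage, and section 7 gives mild physical injury as the one expected adverse event of yoga. For a component that works, the most plausible physical harm is therefore extra injury through extra practice.

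Case-by-case attribution is poorly suited to that pathway. A strain during home practice would naturally be coded to yoga or to study participation. Nothing in the single case shows whether the session would have taken place without a text cue or a payment. Such a component could pass Step 2 with few or no events against its name while injuries were more frequent among those randomised to it. The factorial design can answer the question directly, because half the participants are randomised to each level of every component, but the plan does not ask it.

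**Working it through.** **1. The plan's own figure.** Section 9.2 states power above .80 for d = .40 and above .90 for d = .50 with n = 158, which is 79 per level. In the normal approximation, power = Φ(d·√(n/2) − z).
- d = .40, two-sided alpha .10: .40 × √39.5 = 2.514; 2.514 − 1.645 = 0.869; power .81.
- d = .50: 3.142 − 1.645 = 1.497; power .93.

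Both reproduce. Section 9.2 writes alpha/2 = .10; read literally (two-sided .20), power is .89 and .97, also consistent with the text. The two-sided .10 reading suggests a 90% interval below. Per section 9.6, each level has 192/2 = 96 participants, or 79 after the attrition assumed for dosage.

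**2. What is recorded against what Step 2 names.**

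| Recorded or available | Named in Step 2 item 4 |
|---|---|
| All adverse events, whatever the relationship (7.3) | Only those attributed to a component |
| Perceived cause and relation to study participation (7.3) | Relation to a specific component |
| Randomised on/off contrast, 96 per level (9.6) | No contrast |

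**3. Size of a hidden excess.** The documents give no injury risk, so all risks here are assumptions. Half-width = 1.645 × √[(p0(1−p0) + p1(1−p1))/n].
- 15% off, 25% on, n = 96: expected 14.4 versus 24.0 injured; 1.645 × √(.315/96) = .094.
- Same risks, n = 79: 1.645 × √(.315/79) = .104, so an observed 10-point difference would have an interval that includes zero.
- 10% off, 20% on, n = 96: expected 9.6 versus 19.2; 1.645 × √(.25/96) = .084.

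**4. What a successful component might do.** Step 1 equates SMD 0.40 with 31 minutes per week. Assume a constant injury rate per minute and 30 to 120 minutes per week without the component. The rate ratio is then (30+31)/30 = 2.03 down to (120+31)/120 = 1.26. With p1 = 1 − (1−p0)^ratio and 96 per level:
- p0 = 10%: p1 = 19.3% down to 12.4%; power 57% down to 13% at two-sided alpha .10.
- p0 = 20%: p1 = 36.5% down to 24.5%; power 82% down to 18%.

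**5. What the contrast could detect.** With 96 per level, two-sided alpha .10 and 80% power (two-proportion normal approximation), the detectable risk is 15.9% from 5%, 23.3% from 10%, 36.0% from 20% and 47.4% from 30%. Only large differences are detectable.

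**6. Choice of data source.** Section 7.3 says injuries are asked about whenever a participant attends class. If attendance were 40% off and 60% on (assumed), that is 4.8 versus 7.2 inquiries over 12 weeks, a ratio of 1.5 with no true difference in harm. Component 4 pays for attendance, so the weekly item is confounded with it. Sections 6.2.4 and 7.3 give the SAFTEE to all participants at Month 3, covering the previous three months. Section 6.2.3 adds: "Follow-up assessments will be conducted by research staff who are blind to which arm participants were randomized". The SAFTEE is therefore the better main source.

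**The case against.** The strongest reply is that nothing is hidden. The Step 2 list is open-ended, and section 9.6 says of the decision meeting: "At this meeting we will review all data collected". All events are recorded and the SAFTEE is given to everyone, so the meeting could look at events by component. Item 4 also does not say how relatedness is determined. This stands to the extent that the comparison is not barred and the trial does collect the events. A reader might infer that the plan cannot see this harm, but the documents do not support that. What is missing is a planned comparison. The one adverse event criterion that is written down points to attribution instead.

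A reader might also infer that component attribution is impossible because the SAE coders are blind. That goes too far. Section 7.3 allows a designee, section 6.2.3 provides an unblinded co-investigator and unblinded project managers, and the component decision comes after data collection. The blind status of those who code non-serious events cannot be checked, and mild injuries would fall to them. What remains is that no text assigns component attribution to an unblinded role.

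Nor does the argument apply equally to every component. An injury during a 1:1 session or while following a study video can be linked to that component from the case itself. That is a reason to keep attribution as supplementary information.

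Finally, a randomised contrast is imprecise here, and the weekly injury item would bias it. Both objections stand. They govern how the table should be built and read, and they do not remove the reason for having it.

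**Conclusion.** The point holds as a gap in the selection rule. Step 2 names attributed events only, and neither section 9.6 nor section 7.2 plans a comparison by randomised component. Indirect injury from text cues or incentives would normally not count against those components.

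The possible size depends on injury risks that the documents do not give. With assumed risks of 15% and 25%, the expected excess is 24.0 − 14.4 = 9.6 participants out of 96, with a 90% half-width of 9.4 points (10.4 at 79 per level, if the dosage attrition also applied to the SAFTEE). That attribution would miss most of the excess is a judgement about how such cases are usually coded, not a figure from the plan. This is a cheap improvement to component selection. It is no evidence that any component is harmful.

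**What to change.** Extend Step 2 item 4 in section 9.6 along these lines: for each component, report the number and proportion of randomised participants with any adverse event, any yoga injury and any SAE, component on versus off, regardless of attributed cause, with the risk difference and 90% CI.

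- **Source:** the Month 3 SAFTEE as the main source, with the number interviewed shown at each level. Treat the weekly injury item as supportive and note its link to attendance.
- **Who prepares it:** the unblinded project managers, after data collection.
- **Attribution:** keep case-level attribution as supplementary information for 1:1 sessions and videos, and name the unblinded role that makes it.
- **Reading:** state that the table is descriptive and that an interval including zero does not clear a component.

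The cost is a wording change, with a cross-reference from section 7.2, and one table per component from data already collected. The downside is imprecision, as shown above.
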